4.2. Interim Analysis and Data Monitoring

No interim analyses are planned.

The independent safety monitoring board (DSMB) will periodically review a limited set of unblinded tables, listings, and/or datasets, including all reported AEs, as per its responsibilities described in the DSMB Charter. The objectives of the DSMB meetings are to review the safety outcomes of the study and provide guidance to study sponsor regarding the safety of VM202. The data analyses for the DSMB meetings will be provided to the DSMB members and other participants of the DSMB meeting. For additional information, please see the DSMB Charter.

5. Analysis Populations

- The safety population (SAF) will include all subjects who sign consent for the safety
 extension study. Subjects in the analysis population will be analyzed according to the
 treatment received in the VMDN-003 study, regardless of the treatment assigned at
 randomization. Subjects that sign informed consent but screen fail will still be considered
 part of the safety population and will have their collected safety data summarized.
- The intent-to-treat (ITT) population will include all subjects who sign consent for the safety extension study and who were randomized on the VMDN-003 study. The ITT population will be the primary population used for the efficacy analyses. In such analyses, subjects will be randomized according to their randomized treatment on the VMDN-003 study.
- The modified intent-to-treat (mITT) population will include all subjects who sign consent for the safety extension study and complete the Day 365 visit.

6. General Issues for Statistical Analysis

All safety outputs will be based on the safety population and all listings will be presented by actual treatment received. All efficacy outputs will be presented by randomized treatment on the VMDN-003 study. Unless otherwise stated, table outputs will contain a placebo column and a VM202 column. Table and figure outputs based on the baseline use of gabapentin/pregabalin stratification group will also be provided.

6.1. Statistical Definitions and Algorithms

[figure not shown]
6.1.1. Baseline

In general, the last observation recorded prior to the first dose of study drug in the VMDN-003 study will be used as the baseline observation for all calculations of change from baseline.

The baseline average value of the Daily Pain and Sleep Interference Diary is based on the assessments recorded prior to the screening visit.

6.1.2. Adjustments for Covariates

Not applicable.

6.1.3. Multiple Comparisons

Not applicable.

6.1.4. Handling of Dropouts or Missing Data

The Daily Pain and Sleep Interference Diary is to be completed within 14 days of the 12-month visit. The average 24-hour pain score for a visit will be considered as missing if fewer than 5 of 7 days of Daily Pain and Sleep Interference Diary entries are provided. Sensitivity analyses for the mean change in the average 24-hour pain score will include the following imputation approaches for missing values at 3, 6, 9, or 12 months. It is important to note that over-stratification may result when the total list of pre-specified factors is considered. Under this scenario, the least represented factor will be removed and the imputation will be re-run. This process will be followed until the imputed dataset is complete.

- Multiple imputation: Each missing pain score will be imputed ten times to generate ten imputed complete data sets based on the Markov Chain Monte Carlo (MCMC) method with baseline pain score, 3-month and 6-month pain score, and categorical covariates of baseline use of gabapentin and/or pregabalin, baseline HbA1c, gender, and age. The imputed score will be rounded to the first decimal point. The results of the ten tests from the continuous Repeated Measures Model using these data will be combined.
- Mean of the other group (MOTH)¹ as follows:
 - 1. For a subject with a missing 3-month or 6-month average 24-hour pain score, identify the subject's following baseline characteristics:
 - Study treatment group
 - Baseline use of gabapentin and/or pregabalin.
 - Baseline average 24-hour pain score (< median or ≥ median)
 - HbA1c (< median or ≥ median)
 - Gender (male or female)
 - Age (<65 years and ≥ 65 years).

The median subgroups will be based on the median of ITT subjects in the VMDN-003 study such that VMDN-003b subjects remain in the same subgroups across studies.

2. The missing 3-month, 6-month, 9-month, or 12-month average 24-hour pain score will be imputed by using the mean average 24-hour pain score obtained at the same time point of those subjects in the other treatment group who match the subject's baseline characteristics. For example, for the missing pain scores of the VM202 subjects, the mean pain scores of the placebo subjects within the same

AD-ST-33.05 Effective date: 22-Jan-2018

covariate groups will be used to impute the missing pain scores.

- The baseline characteristics will be re-examined for appropriateness and may be re-categorized (due to small sample size) before unblinding the study.
- 4. The imputed score will be rounded to the first decimal point. The imputed scores will be included in the continuous Repeated Measures Model analysis.

Sensitivity analyses for the percentage of subjects with a reduction in the average 24-hour pain score of at least 50% will include the following imputation approaches for missing values at 3 or 6 months.

- Imputed average 24-hour pain scores at 3, 6, 9, and 12 months from the multiply-imputed pain score datasets described above. The results of the ten tests from the categorical Repeated Measures Model will be combined.
- Missing pain score will be imputed from the MOTH-imputed dataset described above and the categorical Repeated Measures Model will be used for the data analyses.
- Multiple imputation for the missing responder outcomes, 1 (Yes) or 0 (No), by fully
 conditional specification logistic regression method: each missing responder outcome
 will be imputed ten times to generate ten imputed complete data sets using a logistic
 regression model with baseline use of gabapentin and/or pregabalin, and categorical
 baseline HbA1c, gender, and age as covariates. The results of the ten tests from the
 categorical Repeated Measures Model will be combined.

Steps to generate the MMRM analysis are presented below; different options will be used depending on the exact model being run. First the proc mixed code in section 8.1 will be run within each imputation dataset. Least square means, differences between treatments, and p-values will be combined using the following MIANALYZE code.

Proc Mianalyze data=[LS Mean/Difference/p-value dataset from proc mixed];

by avisitn trtn; modeleffects estimate; stderr;

Run:

6.1.5. Analysis Visit Windows

Analyses of all variables for this study will be done by nominal timepoint. No visit windowing will be applied.

6.1.6. Pooling of Sites

Not applicable.

6.1.7. Derived Variables

- The Average 24-hour Pain Score will be derived by taking the average of the daily pain
 measurements recorded by a subject prior to a visit. The score will only be derived if a
 subject completes at least 5 of 7 days of diary entries within the 14 days prior to the visit.
- The Average 24-hour Sleep Interference Score will be derived by taking the average of the daily sleep interference measurements recorded by a subject prior to a visit. The score will only be derived if a subject completes at least 5 of 7 days of diary entries within the 14 days prior to the visit.
- Change from baseline = value at current time point value at baseline.
- Treatment-Emergent Adverse Event (TEAE) = All adverse events collected in the VMDN-003b clinical database with a start date after the last visit on the VMDN-003 study will be considered treatment-emergent.

6.1.8. Data Adjustments/Handling/Conventions

All collected data will be presented in listings. Data not subject to analysis according to this plan will not appear in any tables or graphs but will be included only in the data listings.

Adverse events will be coded using the MedDRA version 21.0 thesaurus.

Concomitant medications will be coded using the World Health Organization Drug Dictionary Enhanced (WHO-DDE) (March 2018).

A treatment related AE is any AE with a relationship to the study drug of possibly, probably, or definitely.

The date and time of the first dose of study drug will be the date and time of the first dose of study drug in the VMDN-003 study.

For partial medication start dates:

- If the year is unknown, then do not impute the date but assign a missing value.
- If the year is known, but the month or month and day is unknown, then:
 - If the year matches the year of first dose date and the end date (if present) is after first dose date, or medication is ongoing, then impute as the month and day of the first dose date. If this produces a date after the medication end date, assign 01 January.
 - Otherwise if the year does not match the year of the first dose date, assign 01 January.
- If the year and month are known, but the day is unknown, then:

- If the month and year match the month and year of the first dose date, then impute as the day of the first dose date. If this produces a date after the medication end date, assign 01.
- Otherwise, if the month and year do not match the month and year of the first dose date, assign 01.

For partial medication end dates:

- If the year is unknown, then do not impute the date but assign as missing value.
- If the year is known but the month or month and day is unknown, then:
 - If the year matches the year of the last date of the study (date of last contact if subject lost to follow-up; date of completion or early termination otherwise), then impute as the month and day of the last date of the study.
 - Otherwise, assign 31 December.
- If the year and month are known, but day is unknown, then:
 - If the month and year match the month and year of the last date of the study, then
 impute as the day of the last date of the study.
 - Otherwise, assign the last day of the month.

For partial AE start dates:

- When the year is known, but the month and day is unknown, then:
 - If the year matches the year of first dose date and the end date (if present) is after first dose date, or AE is ongoing, then impute as the month and day of the first dose date.
 - If the year of AE onset < year of initiation of the treatment, then the month and day will be set to December 31st.
 - If the year of AE onset > the year of initiation of treatment, then the month and day will be set to January 1st.
- When the year and day are present and the month is missing:
 - If the year of AE onset = the year of initiation of the treatment, then the month will be set to the month of initiation of the treatment.
 - o If the year of AE onset < the year of initiation of the treatment, then the month will be set to December.
- If the year and month are known, but the day is unknown, then:
 - o If the year of AE onset = the year of initiation of the treatment and:
 - the month of AE onset = the month of initiation of the treatment, then the day will be set to the day of initiation of the treatment.
 - the month of AE onset < the month of initiation of the treatment, then the day will be set to the last day of month.

- if the month of AE onset > the month of initiation of the treatment, then the day will be set to the 1st day of month.
- If the year of AE onset < the year of initiation of the treatment, then the day will be set to the last day of month.
- If the year of AE onset > the year of initiation of the treatment, then the day will be set to the 1st day of month.

If the imputed AE onset date is after the AE stop date, then the onset date will be set to the stop date.

If an AE has a missing severity, it will be considered severe. If an AE has a missing relationship to study medication, injection procedure, or underlying disease, it will be considered related.

Baseline gabapentin/pregabalin use will be set based on the baseline gabapentin/pregabalin use from the VMDN-003 study.

7. Study Patients/Subjects and Demographics

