5. EVALUATION OF ADVERSE EVENTS

5.1. **DEFINITIONS**

An Adverse Event (AE) is the development of an untoward medical occurrence or the deterioration of a pre-existing medical condition following or during exposure to an investigational product, whether or not considered causally related to the product.

An untoward medical condition can be symptoms (e.g., nausea, chest pain), signs (e.g., tachycardia, enlarged liver) or clinically significant abnormal results of an investigation (e.g., laboratory findings, electrocardiogram).

Conditions or diseases that are chronic but stable should not be recorded as an AE. Changes in a chronic condition or disease that are consistent with natural disease progression are NOT considered AEs and also should not be recorded on AE worksheets. These medical conditions should be adequately documented on the appropriate page of the study worksheet (relevant medical history and/or physical examination). However, medical conditions present at enrollment that worsen in intensity or frequency in a manner inconsistent with the natural course of the disease during the treatment or post-treatment periods should be reported and recorded as AEs.

An adverse reaction means any adverse event caused by a drug. Adverse reactions are a subset of all suspected adverse reactions for which there is reason to conclude that the drug caused the event.

Suspected adverse reaction means any adverse event for which there is a reasonable possibility that the drug caused the adverse event. For the purposes of IND safety reporting, 'reasonable possibility' means there is evidence to suggest a causal relationship between the drug and the adverse event. A suspected adverse reaction implies a lesser degree of certainty about causality than adverse reaction, which means any adverse event caused by a drug.

A serious adverse event (SAE) is any untoward medical occurrence which:

- Results in death:
- Is life-threatening;
- Requires inpatient hospitalization (admission to hospital with a stay > 24 hours) or prolongation of hospitalization which is not specifically required by the protocol or is elective;
- Results in permanent impairment of a body function or permanent damage to a body structure; or
- Requires medical or surgical intervention to preclude permanent impairment of a body function or permanent damage to a body structure.

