9.1. Adverse Events

Adverse events will be coded using the MedDRA coding thesaurus (version 21.0). All AEs recorded in the clinical database starting after the last visit on the VMDN-003 study will be considered a treatment-emergent adverse event (TEAE). All AE summary tables will include the number and percentage of subjects with an AE within a category, system organ class (SOC), and preferred term.

An overall summary of the number and percentage of subjects with TEAEs will be provided by treatment group. Frequencies and percentages of the following will be included: subjects with any TEAE, subjects with any TEAE leading to discontinuation, subjects with any TEAE leading to death, and subjects with any serious treatment-emergent AE (SAE).

The incidence of TEAEs will be summarized with frequencies and percentages by the following:

- SOC and PT
- SOC and PT by maximum severity
- SOC and PT by relationship to study medication
- SOC and PT by relationship to injection procedure.
- SAEs by SOC and PT
- AEs of special interest by SOC and PT

There are 4 types of AEs of special interest (AESI):

- Ophthalmological events that could potentially suggest causality related to HGF and its angiogenic potential
- Acute cardiac events

- Foot ulcers
- AEs related to pregabalin or gabapentin and their occurrence rates with in conjunction with VM202

Adverse event data will be summarized by treatment group and by treatment group within baseline gabapentin and pregabalin use.

All adverse events will be presented in a listing.

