Note: The denominator for percentage corresponds to the N in each column. N is the number of subjects in the safety population. Subjects are summarized by treatment received in the VMDN-003 study.

[1] P-value from a Cochran-Mantel-Haenszel (CMH) test (stratified by baseline use of gabapentin/pregabalin) comparing VM202 to Placebo. SOURCE: Listing 16.2.6.2

[figure not shown]
[figure not shown]

Table 14.2.5.2
Summary of Patient's Global Impression of Change (PGIC) by Gabapentin and/or Pregabalin use at Baseline mITT Population

Same shell as Table 14.2.5.1, add a row at the top of table reading "Group: Gabapentin and/or Pregabalin Use". Once all records from group are summarized, update row text to "Group: No Gabapentin and/or Pregabalin Use" and start table on a new page. Do not include the CMH test or footnote.

Helixmith Co., Ltd. Protocol VMDN-003b

CONFIDENTIAL

Page x of y <Version>

Table 14.3.1.1.1 Summary of Treatment Emergent Adverse Events Safety Population

Category	Placebo (N=XX) n (%)	VM202 (N=XX) n (%)	Overall (N=XX) n (%)
Subjects with at least one TEAE	XX (XX.X%)	XX (XX.X%)	XX (XX.X%)
Subjects with at least one TEAE related to study medication	XX (XX.X%)	XX (XX.X%)	XX (XX.X%)
Subjects with at least one TEAE related to injection procedure	XX (XX.X%)	XX (XX.X%)	XX (XX.X%)
Subjects with at least one TEAE leading to discontinuation	XX (XX.X%)	XX (XX.X%)	XX (XX.X%)
Subjects with at least one TEAE leading to death	XX (XX.X%)	XX (XX.X%)	XX (XX.X%)
Subjects with at least one SAE	XX (XX.X%)	XX (XX.X%)	XX (XX.X%)

Abbreviations: PT = Preferred Term; SOC = System Organ Class; TEAE = Treatment emergent adverse event; SAE = Serious treatment emergent adverse event; N = Number of subjects in the safety population; n = Number of subjects with events.

Note: The denominator for percentage corresponds to the N in each column. Subjects are summarized by treatment received in the VMDN-003 study. AEs were coded using MedDRA version 21.0. A TEAE is any AE that occurs after the last visit in the VMDN-003 study and pre-existing medical conditions that worsen following the last visit in the VMDN-003 study.

SOURCE: Listing 16.2.7.1

[figure not shown]
[figure not shown]

Table 14.3.1.1.2

Summary of Treatment Emergent Adverse Events by Gabapentin and/or Pregabalin use at Baseline Safety Population

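### Partial AE onset dates are imputed from first dose, 1 January or the 1st of the month rather than from the last VMDN-003 visit that opens the TEAE window, so true extension AEs can drop out of the primary-endpoint tables

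*SAP*

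**What the plan says.** **Endpoint.** SAP 2.2.1 and Protocol 5.6.1 make AE occurrence, VM202 against placebo, the primary endpoint. The AE incidence tables in SAP 9.1 and 14.2 are TEAE tables.

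**Window.** SAP 6.1.7 counts as treatment-emergent the AEs in the "VMDN-003b clinical database with a start date after the last visit on the VMDN-003 study". Section 9.1 repeats this.

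**Partial AE start dates (SAP 6.1.8).** The reference date is the first dose in VMDN-003.
- Year only, first-dose year: if the end date is after first dose "or AE is ongoing, then impute as the month and day of the first dose date".
- Year only, later year than "the year of initiation of treatment, then the month and day will be set to January 1st".
- Day missing, later month or later year: "then the day will be set to the 1st day of month".
- The branch headed "When the year and day are present and the month is missing" covers onset years equal to or before the first-dose year. It says nothing about a later year.
- The one override moves an imputed onset back to the stop date if it falls after it.

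**Second definition.** The notes under the TEAE tables (for example Table 14.3.1.1.1) add to new AEs "and pre-existing medical conditions that worsen following the last visit in the VMDN-003 study". Sections 6.1.7 and 9.1 go by start date alone.

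**The concern.** Imputing to the first-dose date is protective when the treatment-emergent window opens at first dose, because a doubtful event is then counted. Here the window opens about 270 days later, and the same rule excludes the event. Nothing in 6.1.8 sets a floor at the last VMDN-003 visit or counts an AE whose partial date could lie in the window.

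Elsewhere the SAP resolves missing information the other way. A missing severity is taken as severe and a missing relationship as related (6.1.8). A medication with no start date is concomitant unless its stop date falls before the treatment start (Table 14.3.7.1 note).

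At stake is the count behind the primary endpoint. An event that fails the date test leaves every TEAE table and survives only in Listing 16.2.7.1. Partial dates are plausible because the extension has a single visit, about 95 days after Day 270.

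The two TEAE definitions are a lesser point. They give different counts for an AE that began in VMDN-003, worsened later and is carried forward under its original date.

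**Working it through.** The plan gives no figure to reproduce, so the 6.1.8 rules were applied to every case in a grid.

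**Inputs.** From the documents: the window opens after the last VMDN-003 visit, taken as Day 270, and the extension visit is at Day 365 ± 14. Assumed: Day 0 is uniform over a 365-day year, Day 270 is on time, onset is uniform over Days 271 to 365, and the stop date does not interfere. The grid has 365 Day 0 dates × 95 onset days = 34,675 cases. An AE is lost if its imputed onset is on or before Day 270.

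**Year only.**
- For Day 0 on or after 6 April (270 of 365 dates), Day 270 falls in the next calendar year, so 1 January of that year is not after it and all 95 onsets are lost: 270 × 95 = 25,650 (74.0%).
- For the other 95 dates, onsets still in the first-dose year are set to Day 0: 94 + 93 + … + 1 = 94 × 95 / 2 = 4,465 (12.9%).
- Total: 30,115 / 34,675 = 86.8%.
- Window ending Day 351: 26,244 / 29,565 = 88.8%. Window ending Day 379: 33,790 / 39,785 = 84.9%.

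**Day missing.** The loss is exactly the onsets in the calendar month of the last visit. Summing m(m − 1)/2 over months of m days: 7 × 465 + 4 × 435 + 378 = 5,373, and 5,373 / 34,675 = 15.5%. For windows ending Day 379 and Day 351 the share is 13.5% and 18.2%. Other day-missing dates are classed correctly.

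**Month missing, day known.**

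| Result | Cases | Share |
|---|---|---|
| Later year, no rule | 30,210 | 87.1% |
| First-dose month used, onset before the cut-off | 4,318 | 12.5% |
| Impossible calendar date | 147 | 0.4% |
| Counted as TEAE by a stated rule | 0 | 0% |

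**Direction.** For onsets on Days 0 to 270 (365 × 271 = 98,915 cases), the year-only and day-missing rules wrongly count none. The error for these two patterns is one-sided.

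**Example.** Day 0 is 15 June 2018, so Day 270 is 12 March 2019. An AE starting 20 March 2019 with the day missing becomes 1 March 2019 and is dropped.

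**Effect on the total.** If 1% to 10% of extension AEs lack only the day (an assumption), the loss is 0.01 × 15.5% to 0.10 × 15.5%, about 0.15% to 1.5% of extension AEs.

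**The case against.** **Year-only dates should be rare.** Events are taken in person about 95 days after Day 270, the AE form asks for an onset date, and monitors and computerized checks raise queries (Protocol 5.2, 12). This stands: 86.8% is a share of a class that may be small, and day-missing dates are the likelier case.

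**The calendar drives the year-only result.** By month of Day 0, the loss is 21% for March, 52% for February, 83% to 84% for January and April, and 100% from May to December. This also stands. Varying only the window end gives too narrow a range, and the real distribution of Day 0 is not in the documents.

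**The tables count subjects.** A lost AE changes the any-TEAE row only if the subject has no other TEAE, so subjects lost cannot exceed AEs lost.

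**Having no rule is not the same as excluding.** Correct for the 87.1%: those cases are left to the programmer.

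**Re-anchoring can add more than it rescues.** At a constant daily AE rate, with all Day 0 to 270 AEs held in the VMDN-003b database and no stop date to exclude them, year-only dates would gain 62,059 earlier onsets against 30,115 rescued. Month-missing dates would gain 57,880 against 34,675, and day-missing dates 5,373 against 5,373. Protocol 5.3 collects AEs from Day 0, so this is possible. It is a reason to flag imputed events and show both counts, not to keep a rule that errs one way without showing it.

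**The consequences are limited.** Both arms follow the same rule, the protocol plans descriptive analyses only, and the events are listed. This bounds the severity.

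**The definitions can be read together.** Protocol 5.1 already treats "the deterioration of a pre-existing medical condition" as an AE, so a worsening may carry its own start date. The definitions then differ only for AEs carried forward under the original date.

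**Conclusion.** The concern holds and should be fixed. Followed exactly, the SAP dates some true extension AEs before the window opens and removes them from the primary-endpoint tables. Under the uniform-date assumptions the loss is 86.8% of year-only and 15.5% of day-missing extension onsets, and no stated rule counts a month-missing one. The year-only figure depends strongly on the calendar date of Day 0.

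The effect on overall incidence cannot be sized, because the documents do not say how many onset dates will be partial; if few are, it is small. The consequence to expect is understated incidence in both arms rather than bias towards one. The mismatch between the rules and the window, and the missing rule for a later year, do not depend on any assumption.

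**What to change.** 1. In SAP 6.1.8, for AEs in the VMDN-003b database: where the known date parts allow onset after the last VMDN-003 visit and the stop date does not rule it out, impute the earliest date after that visit that fits the known parts. Apply this to year-only, day-missing and month-missing dates. In the grid above it loses 0 of 34,675 for each pattern.
2. Flag AEs with imputed onset, and show the any-TEAE row with and without AEs counted only because of imputation.
3. Use one TEAE definition, new or worsened after the last VMDN-003 visit, in 6.1.7, 9.1 and the table notes. Keep the protocol-defined safety population as denominator.

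**Cost.** SAP wording, a few lines of programming and one table row. The downside is over-inclusion. Among AEs with onset on Days 0 to 270 that sit in the VMDN-003b database with no excluding stop date, up to 5.4% (5,373 / 98,915, day missing), 58.5% (57,880 / 98,915, month missing) or 62.7% (62,059 / 98,915, year only) would be added. Querying partial dates and checking them against VMDN-003 AE records would reduce this, and the with/without row shows what remains.
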